Long title	A non-interventional, mixed-methods, prospective cohort study to characterise the real world implementation, roll out, safety and patient experience of the long-acting injectable HIV treatment regimen of 2-monthly cabotegravir and rilpivirine	
Funder	ViiV Healthcare	
Rationale	The long-acting (LA) injectable antiretroviral therapy regimen of cabotegravir and rilpivirine (LA CAB+RPV) given 2-monthly is a remarkable, promising and widely welcomed paradigm shift in HIV treatment. However, there are currently no real-world data on the implementation strategies planned in different clinical settings, the feasibility and acceptability of LA CAB+RPV to patients and clinicians, nor clinical outcomes with the regimen outside of clinical trial settings.	
	Based on British HIV Association guidelines on the use of the injectable regimen it is currently not known what proportion of people living with HIV (PLWH) in the UK would be eligible for LA CAB+RPV nor how many considered eligible will be offered the regimen, and how many of those offered will actually take it up. Characterising this adoption cascade, as well as the individual and system-related factors at play, is important as it will enable a better understanding of the ultimate uptake and impact of LA CAB+RPV	
Primary objectives	1. ADOPTION: To quantify the LA CAB/RPV adoption cascade	
Secondary objectives	 2. ACCEPTIBILTY: a. To explore the acceptability of LA CAB+RPV amongst PLWH and health care workers delivering the regimen through a participant questionnaire, healthcare practitioner questionnaire and qualitative research. b. To compare patient-reported outcomes including quality of life, treatment satisfaction and treatment preference in those on LA CAB+RPV compared to those who remain on oral ART (demographically similar but not eligible for LA ART) 	
	3. FEASIBILITY:	
	 a. To describe feasibility of the regimen through outcomes in the participant and healthcare practitioner questionnaires 	
	 b. To explore barriers and facilitators to effective implementation of LA CAB+RPV 	

	 4. FIDELITY: To describe the fidelity of regimen delivery and associated monitoring compared to intended use in BHIVA guidelines 5. EFFECTIVENESS: a. To characterise the UK-wide population who are switched to LA CAB+RPV and indications for switch b. To describe virological and clinical outcomes at one year of therapy in those on LA CAB+RPV and in those remaining on oral ART (demographically similar but not eligible for LA ART) c. To identify where actionable adjustments to implementation can be made to optimise overall adoption, sustainability and effectiveness of LA CAB+RPV 	
Primary outcome	1. ADOPTION:	
measures	a. Proportion of clinical cohort eligible for LA CAB+RPV according to BHIVA guidance	
	b. Proportion of eligible adults offered/discussed a switch to LA CAB+RPV	
	c. Proportion who accept the switch to LA CAB+RPV	
	d. Proportion who remain on LA CAB+RPV at one year and	
	reasons for switching off the regimen	
Design	This is a mixed methods, non-interventional, multi-centre,	
	prospective observational study with a nested qualitative	
Deputation	component at UK NHS HIV treatment centres.	
Population	Approximately 10-20 adults receiving LA CAB+RPV and 5-10 matched controls on oral ART will be included from each	
	participating centre	
Duration	Each participant in the observational cohort study will contribute	
Daration	at least 1 year of longitudinal data to the study.	
	The total duration of the study at each participating HIV centre	
	will be 2 years to allow time for recruitment and follow-up.	
	The total duration of the study at the Coordinating Centre will be	
	3.5 years to allow time for study set up followed by data	
	collection, cleaning and analysis.	
Statistical methods	This is primarily a descriptive study. Descriptive statistics will be	
	·	
Sample size		
Jumpic 312C	·	
	adults who remain on oral ART as the comparator population.	
Sample size	used explain the demographics, clinical and treatment characteristics of all participants (age, BMI, race/ethnicity, comorbidities, ART history). Data will be presented as summary statistics as appropriate (mean, median, standard deviation, IQR, maximum and minimum for continuous measurements, and numbers and proportions for categorical measurements). Across all study sites the aim is to recruit a minimum of 150 adults receiving LA CAB+RPV into the prospective cohort study and ~50 adults who remain on oral ART as the comparator population	

Around 20-30 participants will participate in the nested
qualitative study.
Around 30 healthcare workers will contribute data through focus
group discussions and questionnaires

7. Background and Rationale

The long-acting injectable antiretroviral therapy regimen of cabotegravir and rilpivirine (LA CAB+RPV) given 2-monthly is a remarkable, promising and widely welcomed paradigm shift in HIV treatment [1-4]. The regimen was recently approved by the National Institute for Clinical Excellence (NICE) and roll out is underway in the United Kingdom (UK) National Health Service (NHS) [5]. Current trial data suggest it is an efficacious regimen and is well-liked by the majority of trial participants [1-4][6]. There are multiple advantages over traditional oral antiretroviral therapy, such as it being less user-dependent, removing the burden of daily pill-taking, and being more easily concealed, reducing concerns around stigma [7].

Outside of trials, to date LA CAB+RPV has only been used in select circumstances on compassionate grounds in small numbers of individuals unable to take oral therapy. Therefore, there are currently no real-world data on the implementation strategies planned in different clinical settings, the feasibility and acceptability of LA CAB+RPV to patients and clinicians, nor clinical outcomes with the regimen outside of clinical trial settings [8, 9]. HIV services throughout the UK are currently planning and executing local roll out of LA ART but it is not yet known how this will be individualised based on patient needs and service capacity. Clinical trial data does not address the practical needs of the stakeholders responsible for introducing the intervention and more data are urgently needed in this area. This is especially pertinent to LA CAB+RPV considering it requires increased frequency of visits and HIV viral load (VL) monitoring, adequately trained clinical staff, robust injection appointment management systems, oral bridging in events of delayed injections and all this must be incorporated into existing clinic work streams and human resources [10].

The British HIV Association (BHIVA) have released guidance on eligibility for LA ART based on the following nine criteria [9]:

- 1. significant need for injectable antiretroviral therapy;
- 2. viral suppression for at least 6 months;
- 3. no known or suspected NNRTI or INSTI resistance;
- 4. no history of virological failure or unplanned treatment interruption on NNRTI or INSTI-containing ART regimens;
- 5. no prior history of INSTI monotherapy;
- 6. ability to tolerate and commit to a 2-monthly attendance schedule for injections;
- 7. accepting of small risk of virological failure despite complete adherence;
- 8. BMI <30 kg/m² AND non-A1/A6 subtype if baseline resistance unavailable;

9. not requiring a tenofovir-based regimen for treatment or prevention of hepatitis B virus

BHIVA also recommend that those who started on LA CAB+RPV in a clinical trial or as part of a compassionate access programme may continue it. Additionally, HIV VL monitoring is recommended at every visit, with prompt recall advised in cases of viral rebound due to concerns about rapid emergence of 2-class resistance [9].

Based on the above criteria, it is currently not known what proportion of PLWH in the UK today would be eligible for LA CAB+RPV and it is possible that the numbers will vary across different demographic groups and settings. It is also not clear how many PLWH considered eligible will be offered the LA CAB+RPV regimen, and how many of those offered LA ART will actually take it up. Characterising this adoption cascade, as well as the individual and system-related factors at play, is important as it will enable a better understanding of the ultimate uptake of LA CAB+RPV.

As current efficacy data are largely from clinical trials, adherence to injection schedules may have been greater than that which will be observed in real-world settings. It will be prudent to assess whether adherence to the treatment regimen is replicated in real world settings, or whether instances of PLWH requiring bridging oral therapy are more frequent, and how this would be operationalised. Local strategies used to support timely administration of injections can be described and may require scaling up alongside the regimen roll out e.g. text reminders, App-based mobile health technology, use of community support workers.

In summary, there are currently no real-world data available on implementation approaches being adopted in UK HIV services, barriers and facilitators to the widespread uptake of LA CAB+RPV, acceptability of the regimen amongst clinicians and PLWH, and virological outcomes. Information on adoption, acceptability, fidelity and effectiveness will be important to guide policymakers, commissioners, HIV services, other stakeholders and PLWH in the optimal roll-out of LA CAB+RPV in the UK.

8. Hypothesis

There are likely to be challenges in the implementation of LA CAB+RPV as part of routine clinical care in real-world settings; characterising these barriers will aid the development of strategies to overcome them. However, high levels of effectiveness and acceptability will be demonstrated in those who do switch to LA CAB+RPV in a real-world setting.

9. Objectives

9.1. Primary Objective

1. ADOPTION: To describe the strategies being deployed in different UK HIV services to deliver LA CAB+RPV and to quantify the adoption cascade in terms of what proportion of each clinic cohort are: a) eligible for LA CAB+RPV in accordance with BHIVA

guidelines; b) have a switch to LA CAB+RPV discussed; c) accept a switch to LA CAB+RPV; and to ascertain reasons for attrition at each step of the cascade (Fig. 1).

[figure not shown]

Figure 1. Adoption cascade

9.2. Secondary Objectives

2. ACCEPTABILITY:

- a. To explore the acceptability of LA CAB+RPV amongst PLWH and health care workers delivering the regimen through a participant questionnaire, healthcare practitioner questionnaire and qualitative research.
- b. To compare patient-reported outcomes including quality of life, treatment satisfaction and treatment preference in those on LA CAB+RPV compared to those who remain on oral ART (demographically similar but not eligible for LA ART)

3. FEASIBILITY:

- c. To describe the feasibility of using the regimen from a clinical and patient perspective through outcomes in the participant and healthcare practitioner questionnaires
- d. To explore barriers and facilitators to effective implementation of the LA CAB+RPV regimen
- **4. FIDELITY:** To describe the fidelity of regimen delivery and associated monitoring compared to intended use in BHIVA guidelines

5. EFFECTIVENESS:

e. To characterise the UK-wide population who are switched to LA CAB+RPV and indications for switch

- f. To describe virological and clinical outcomes at one year of therapy in those on LA CAB+RPV and in those remaining on oral ART (demographically similar but not eligible for LA ART)
- g. To identify where actionable adjustments to implementation can be made to optimise overall adoption, sustainability and effectiveness of LA CAB+RPV

10. Outcome Measures

There are no interventional components to the study. Service-specific approaches to implementation of LA CAB+RPV in use at the study sites at study outset will be described, contrasted and compared.

Objective	Outcome measures	
Implementation outcomes		
ADOPTION 1. To quantify the adoption cascade	 a. Proportion of clinical cohort eligible for LA CAB+RPV according to BHIVA guidance b. Proportion of eligible adults offered/discussed a switch to LA CAB+RPV c. Proportion who accept the switch to LA CAB+RPV d. Proportion who remain on LA CAB+RPV at one year and reasons for switching off the regimen 	
ACCEPTIBILITY 2a. To explore the acceptability of LA CAB+RPV amongst PLWH and health care workers delivering the regimen through a participant questionnaire, healthcare practitioner questionnaire and qualitative research. 2b. To compare patient-reported outcomes including quality of life, treatment satisfaction and treatment preference in those on LA CAB+RPV compared to those who remain on oral ART (demographically similar but not eligible for LA ART)	 a. The acceptability and experiences of the regimen amongst participants (PLWH) and healthcare workers delivering LA CAB+RPV through outcomes in the participant and HCP questionnaires b. The patient reported outcomes will be described through: i. Outcomes in the participant questionnaire and treatment preference in those switched to LA CAB+RPV ii. HIV-related quality of life - HIVPROM (11) 	
FEASIBILITY	a. Outcomes in the healthcare worker and participant questionnaires	

	CORAL
3a. To describe feasibility through outcomes in the participant and healthcare practitioner questionnaires 3b. To explore barriers and facilitators to effective implementation	b. Experiences, barriers and facilitators at both the individual and service level from qualitative work
FIDELITY	 a. Proportion of injections delivered within the visit window b. Number of oral bridging courses per patient per year c. Fidelity to 2-monthly HIV viral load monitoring (+/- 2 weeks of target date)
Effectiveness outcomes	
EFFECTIVENESS 5a. To characterise the UK-wide population who are switched to LA CAB+RPV and indications for switch 5b. To describe virological and clinical outcomes at one year of therapy in those on LA CAB+RPV and in those remaining on oral ART (demographically similar but not eligible for LA ART)	 a. Proportion of those who begin LA CAB+RPV who remain virologically suppressed at 12 months (by FDA snapshot algorithm and intention to treat approach), and the proportion of those on oral ART who remain virologically suppressed at 12 months after the baseline date b. Proportion of each group who have experienced virological failure at 12 months c. HIV-related medical events at 12 months d. Change in CD4 count from baseline to month 12 (where available) e. Change in renal function (estimated glomerular filtration rate, eGFR) from baseline to month 12
5c. To identify where actionable adjustments to implementation can be made to optimise overall adoption, sustainability and effectiveness of LA CAB+RPV	At the conclusion of the study, lessons learned about barriers and facilitators to effective implementation will be reported. Actionable interventions which services can use to optimise adoption and overall effectiveness of the regimen will also be proposed

11. Methodology

11.1. Study design

This is a non-interventional, multi-centre, prospective observational study with a nested qualitative component at UK NHS HIV treatment centres. The study is being coordinated by a research team at Brighton and Sussex Medical School which is part of the University of Sussex. The individual components of the study are described separately below:

11.1.1. Observational study using routinely collected clinic data

The study will capture data from HIV-1 positive adults receiving long-acting cabotegravir and rilpivirine as part of their treatment regimen. All HIV-1 positive adults (≥ 16 years) who initiated long-acting cabotegravir and rilpivirine-based ART any time from 6 months prior to study site initiation will be eligible to be included in this study. A demographically similar comparator group on oral ART will also be invited to join the study. Routinely collected medical data from eligible and consenting participants' medical records will be extracted at key intervals, as laid out in the Schedule of Activities (see section 12.3.4), and entered into an electronic data capture system (Research Electronic Data Capture, REDCap). Variables of interest include demographic data, HIV treatment history, laboratory findings, which are all collected routinely in line with the BHIVA monitoring guidelines.

The total duration of patient follow-up is at least 1 year from the time of enrolment. The final analysis will be conducted following database lock after the last study participant has reached the 12 months treatment milestone and all data queries have been resolved.

Patients who received LA ART outside of the BHIVA criteria e.g. on compassionate grounds are of interest and can be included in the prospective study; the reasons for BHIVA criteria ineligibility and outcomes (duration of therapy, virological and clinical) will be described.

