11.2. Study population

The study will be conducted in approximately 10-12 NHS HIV departments in the UK (4-5 in England, 1-2 in Wales, 1-2 in Scotland and 1 in Northern Ireland). To ensure the data are representative of the UK, participating clinics will be distributed across England, Wales, Scotland and Northern Ireland and of varying cohort size (small, medium and large), geographical area (urban; rural) with a diverse clinic population. It is anticipated that 5-20 patients in LA CAB+RPV and 3-6 patients on oral ART will be enrolled from each centre depending on cohort size. Patients who were initiated on LA CAB+RPV within the prior 6

months will be identified by a member of the clinical team or research team, from review of clinic records and databases as appropriate at each centre. Patients beginning LA CAB+RPV in the 6-12 months after site initiation will be eligible to join prospectively.

It is intended that approximately 10-20 patients on LA CAB+RPV and 5-10 controls will be included from each participating centre to represent a proportionate spread from the study sites, but this will be dependent on local LA CAB+RPV uptake. Oversampling may be performed in the larger centres in order to maintain an overall sample size of up to $^{\sim}150$ on LA ART.

In addition, approximately three healthcare workers in different roles at each participating clinic will be interviewed and asked to complete a questionnaire.

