11.2.1. Inclusion criteria for observational study using routinely collected clinic data

- 1. Understands the participant information and study requirements and has capacity to consent.
- 2. Willing to comply with study procedures
- 3. Age 16 years or above
- 4. Is a member of one of the following groups:
 - LA group PLWH who have been recently switched (within the prior 6 months) or are prospectively switched to LA CAB+RPV during the enrolment period. This includes those who have received LA CAB+RPV outside of BHIVA criteria or on compassionate grounds.
 - Oral ART group PLWH who are demographically similar but not eligible for LA CAB+RPV according to BHIVA eligibility criteria and who continue oral ART within the study period (e.g. those who are HBVcoreAb+ or who have an underlying drug resistance mutation that precludes use of LA CAB+RPV). Intervention group to oral group will be matched 3:1 by calendar period and other key variables where possible.

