12.3. Prospective observational study

12.3.1. Collation of routinely collected clinic data

Routine blood testing is performed as part of routine clinical care per the BHIVA HIV Monitoring Guidelines [9]. No research blood testing is performed. Routinely collected clinic data from the participants in the LA CAB+RPV group and oral ART comparator group will be submitted by the participating clinic investigator (research nurse or research assistant) at

baseline, 6 and 12 months via a REDCap case report form. HIV viral load will be collected at every time point that it is measured from the time of participant enrolment.

It is possible to include data on consenting adults who started the injectable regimen up to 6 months prior to the clinic being activated as a study site. These individuals will not be asked to complete the participant questionnaires but their routinely collected clinic data is still valuable to the study objectives.

Continuation of the cohort study period for a longer duration may be possible if funding is made available for cohort and data management. Participants would be contacted to ask whether there are willing for their routinely collected clinic data to be shared beyond the initial 12-month data collection period. This would not involve any additional procedures for the participant.

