12.3.4. Schedule of Activities

The following activities will take place for PLWH enrolled in the prospective cohort study.

Table 1. Schedule of Activities for Participants

·	individual baseline M0*	Individual month 6 (+/- 2 months)	Individual month 12 (+/- 2 months)
Informed consent process	Х		
ROUTINELY COLLECTED CLINIC DATA			
Baseline characteristics, height	X		
Comorbidities	Х	Х	Χ
HIV / ART history	Х		
HIV VL (all interim VLs collected)	Х	X	Χ
CD4+ T cell count (if available)	Х	X	Χ
Creatinine, eGFR, HbA1c, lipids, ALT, weight (if available)	X	X	X
Interim medical events requiring medical attention/treatment		X	X
QUESTIONNAIRES			
Participant questionnaire: • Section A: LA CAB+RPV treatment experience and preference • Section B: HIV PROM (oral comparator group only complete section B)	Х	X	Х
QUALITATIVE			
In-depth interviews (~n=3 at each site)		X	

^{*}Individuals who have been switched to LA CAB+RPV during the 6 months prior to the clinic site being opened for enrolment are eligible to join the prospective cohort study for the collection of routine clinic data. Their individual baseline is the date that they were switched to LA CAB+RPV.

eGFR = estimated glomerular filtration rate, ALT = alanine transaminase, HbA1c = haemoglobin A1c, HIV VL = HIV viral load, HIV PROM = HIV patient reported outcome measures

Approximately three healthcare workers from each participating clinic will be asked to complete a single questionnaire and engage with an interview / focus group discussion.

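### The cohort's follow-up clock contradicts itself, and no rule requires LA starters to consent before their 12-month result is known

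*Protocol*

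**What the plan says.** **Look-back.** Three places in the protocol tie it to the opening of the site. Section 11.1.1 admits adults "who initiated long-acting cabotegravir and rilpivirine-based ART any time from 6 months prior to study site initiation will be eligible". Section 12.3.1 includes consenting adults who "started the injectable regimen up to 6 months prior to the clinic being activated as a study site". The footnote to Table 1 (12.3.4) reads "Individuals who have been switched to LA CAB+RPV during the 6 months prior to the clinic site being opened for enrolment are eligible".

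The inclusion criterion that sites screen against (11.2.1, criterion 4) describes the LA group as "PLWH who have been recently switched (within the prior 6 months) or are prospectively switched to LA CAB+RPV during the enrolment period", without saying prior to what. Section 11.2 repeats the six-month look-back, also without a reference date, and adds: "Patients beginning LA CAB+RPV in the 6-12 months after site initiation will be eligible to join prospectively".

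**Follow-up.** Section 11.1.1: "The total duration of patient follow-up is at least 1 year from the time of enrolment". The Table 1 footnote, on people switched before opening: "Their individual baseline is the date that they were switched to LA CAB+RPV". The last scheduled visit in that table is month 12, plus or minus 2 months.

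**Viral loads.** Section 12.3.1 collects every viral load measured from enrolment onward. Table 1 says that all interim viral loads are collected.

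**Outcomes.** Section 10 lists, among the secondary effectiveness outcomes, the proportion of LA starters still suppressed at 12 months and the proportion with virological failure by then. Section 12.2 requires individual consent before any study procedure.

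**The concern.** Two clocks run in one cohort. Counting from enrolment and counting from the switch give different follow-up for anyone who consents after switching, and the protocol uses both. The viral load wording has the same split. For a pre-opening starter, results between switch and consent are in scope under Table 1 but not under 12.3.1, although they bear on failure by month 12.

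The second problem is what the site-opening look-back leaves unsaid. It limits how early a person may have switched, but not how late that person may consent. Someone can therefore join a cohort described as prospective when the 12-month outcome has already occurred. Because consent is individual, starters who died, moved away or lost contact before being approached cannot be included. The denominator of the 12-month proportions is then no longer everyone who began the regimen. A missing reference date in the criterion that 10-12 centres apply adds room for the intake to differ between sites.

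**Working it through.** Let site initiation be month 0, *s* the month of the LA switch and *e* the month of consent.

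**Inputs**
- Earliest start: *s* = −6 (11.1.1, 12.3.1, 12.3.4).
- Baseline for pre-opening starters: the switch date (12.3.4).
- Last visit: month 12 ± 2, so months 10 to 14 after baseline (12.3.4).
- Follow-up promised: at least 12 months from enrolment (11.1.1).
- Site duration: 2 years for recruitment plus follow-up (Section 6, Protocol Summary).
- Close of enrolment: not stated.

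**Step 1. The plan's own figure.** If the last start is at site month 12 and follow-up is 12 months, the site runs 12 + 12 = 24 months, which matches the stated 2 years (26 with the visit window). A last start at month 6 would need only 18 to 20. Enrolment open to about month 12 is therefore consistent with the document, but it remains an assumption.

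**Step 2. Follow-up left after consent.** Time to month 12 is 12 − (*e* − *s*). For *s* = −6 and *e* = 0 this is 12 − 6 = 6 months, or 14 − 6 = 8 to the end of the window. The promise is 12. With the switch as baseline, the promise fails even at the latest permitted visit once the switch-to-consent gap exceeds 14 − 12 = 2 months.

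**Step 3. Viral loads for the same person.** The 6 months before consent hold about 6 / 2 = 3 measurements at the 2-monthly interval used in the fidelity outcome. Under 12.3.1 they are not collected; under Table 1 they are.

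**Step 4. Time on LA at consent.** All these people meet the site-opening look-back.

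| Switch *s* | Consent *e* | Months on LA at consent | Months left to month 12 |
|---|---|---|---|
| −6 | 0 | 6 | 6 |
| −5 | +3 | 8 | 4 |
| −6 | +4 | 10 (window opens) | 2 |
| −6 | +6 | 12 | 0 |
| −1 | +12 | 13 | none |
| −6 | +12 | 18 | none |

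The gap is not confined to pre-opening starters. A person switching at month 0 and consenting at month 12 also has 12 months on treatment.

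**Step 5. How often (illustration only).** Assume that pre-opening starts are uniform over −6 to 0 and that consent is uniform and independent of the start.
- Consent over 0 to 12: the share at or past month 12 is (6²/2)/(6 × 12) = 18/72 = 25%. The share at or past month 10 is (2 × 6 + 6²/2)/72 = 30/72 = 42%.
- Consent over 0 to 6: past month 12, none beyond the boundary. At or past month 10, (2²/2)/(6 × 6) = 2/36 = 6%.

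The size depends on the length of enrolment, which the protocol does not fix.

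**The case against.** The strongest reply is that the entry window is consistent. Sections 11.1.1, 12.3.1 and 12.3.4 all count from site opening, under three names for the same event. The unanchored phrases in 11.2 and 11.2.1 stand close to site initiation or the enrolment period and can be read the same way. This stands. A reader might infer that one patient is both eligible and ineligible, for example someone who switched at month −5 and is approached at +3. That needs the six months to be counted back from screening, which no section says. What remains is an operative criterion without a reference date.

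A reader might also infer that 11.2 shuts out people starting in the first six months after opening. The sentence states who may join and excludes nobody. A recruitment period of 6 to 12 months is the more natural meaning, and it agrees with 11.1.1 and 11.2.1. The wording is loose, but it does not create a gap in intake.

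It might further be inferred that late consenters are selected for having done well. Criterion 4 requires a switch, not staying on the regimen, so people who stopped or failed can still consent, and Section 14 keeps those lost after enrolment. The selection is the weaker one of being alive, contactable and willing.

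Finally, retrospective capture is declared in 12.3.1, the 18 months is a worst case, and the follow-up conflict is softened in two places. Section 11.1.1 ties the final analysis to the 12-month treatment milestone, and the Protocol Summary asks only for a year of longitudinal data, which switch-dated records can supply. All fair. But declaring retrospective entry does not explain why the switch-to-consent interval has no limit, and the sentence promising a year from enrolment still conflicts with Table 1.

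**Conclusion.** The point holds in three parts.

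1. The follow-up clocks conflict, and no assumption is needed to show it. The earliest starter consenting on opening day has 6 months to the last visit (8 with the window) against 12 promised. The viral load wording in 12.3.1 and Table 1 conflicts in the same way.
2. The reference date is missing from inclusion criterion 4 and from 11.2, and the prospective window in 11.2 is loosely worded. This is a defect of clarity, not a forced contradiction.
3. Nothing requires consent before month 12 on treatment. The maximum gap is 18 months if enrolment stays open to site month 12. If it closes at month 6, the maximum is 12 months and almost nobody passes month 12 before consent. How often late consent will happen is unknown, and the 25% is an illustration under uniform timing.

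The exposure is limited to the secondary, descriptive cohort outcomes, chiefly 12-month suppression and virological failure. The primary adoption cascade, including one-year retention, comes from the clinic registry (11.1.5 and 12.6), which does not depend on this window. The matter should be corrected, but it does not threaten the primary objective.

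**What to change.** - Use site opening as the single reference date for the look-back in 11.1.1, 11.2, 11.2.1, 12.3.1 and the Table 1 footnote.
- In 11.2, let prospective starters join from site initiation to the close of enrolment, and state that closing date.
- Require every LA participant, whether started before or after opening, to consent before their own month-12 window opens, that is, before month 10 after the switch. A limit on pre-opening starters alone would leave the month-0 starter who consents at month 12.
- Replace the promise of a year from enrolment with follow-up to 12 months from the switch date (LA group) or the baseline date (oral group).
- State in 12.3.1 that viral loads from the switch date onward are collected.
- Record the switch-to-consent interval, and report 12-month outcomes separately for retrospective (pre-opening) and prospective starters.

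The cost is protocol wording, one derived variable and the loss of some late-consenting starters. The loss should be small if sites approach pre-opening starters first: the deadline is site month −6 + 10 = +4 for the earliest of them and +10 for someone who switched at opening. If consent were instead spread evenly over 12 months, Step 5 suggests that up to 42% of pre-opening starters would miss it. The limit reduces the selection but does not remove it, since starters lost between switch and consent are still absent. Hence the separate reporting.
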